Belimumab and placebo will be supplied as open-label vials and 3rd party unblinding will be employed. The study agent will be reconstituted and diluted by the unblinded site pharmacist or designee, independent of the study (person responsible for receiving and dispensing study agent). Separate monitors will be responsible for the clinical (blinded monitor) and study agent (unblinded monitor) aspects of the study.

If a medical emergency occurs and a decision regarding the subject's condition requires knowledge of the treatment assignment, the study blind may be broken for the specific subject. Whenever possible, the investigator should consult with the principal investigator of the study and data safety monitoring board prior to unblinding any subject. Any broken blind will be clearly justified and explained. The lead site and sponsor must be notified of any broken blind regardless of whether it was done for emergency or non-emergency reasons.

e. Concurrent Medications:

Corticosteroids: Patients that are on glucocorticoids at the time of screening will be required to be on a stable background dose for at least 2 weeks prior to screening (prednisone (or equivalent) dose \leq 15 mg daily).

The prednisone dose will remain stable until week 24 of the study, at which time a taper will be allowed at the discretion of the site investigator and principal investigator.

An increase in the dose of oral prednisone will be permitted, if clinically necessary, during the first 8 weeks after randomization without accounting it as a disease flare. In this case, the dose of prednisone must be tapered (to less than or equal to 25% of the baseline dose) by week 12. However, if the dose of prednisone cannot be tapered by week 12, the event will be considered as disease flare at that time.

Any increase of the prednisone dose after week 8 for IIM disease activity or the use of pulse steroids at any time during the study will be considered a disease flare. An increase of the prednisone dose at any time during the study for an event other than worsening of IIM disease activity will require the patient to return to the baseline dose of prednisone within 10 days, without accounting the event as a disease flare. Patients that are considered treatment failures will be allowed to remain in the study, in respective groups, at the discretion of the treating physician and PI.

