Immunosuppressive agents (IS): Enrolled patients could have had a history of treatment with any of the following IS agents: azathioprine, methotrexate, mycophenolate mofetil, leflunomide,

tacrolimus, cyclosporine, cyclophosphamide, Rituximab, or intravenous gamma globulin [IVIG]. Patients are not required to be on an IS agent at the time of enrollment.

During the enrollment and study period, the only allowed IS agents are: azathioprine, methotrexate, mycophenolate mofetil, tacrolimus, cyclosporine or intravenous gamma globulin [IVIG].

Patients that are on background immunosuppressive (IS) therapy at the time of screening will be required to be on a stable IS agent for \geq 2 months prior to screening (\geq 3 months for IVIG), and on a stable dose of IS agent for \geq 2 weeks prior to screening (except IVIG; no dose change allowed). Dose reduction due to poor tolerance of IS agent will be allowed on a case by case basis.

Therapeutic Agent	Treatment Duration prior to Screening \geq	Dose Increase prior to Screening \geq
Azathioprine	2 months	2 weeks
Methotrexate	2 months	2 weeks
Mycophenolate mofetil	2 months	2 weeks
Tacrolimus	2 months	2 weeks
Cyclosporine	2 months	2 weeks
IVIG	3 months	none

If a dose increase in IS agent or initiation of a new IS agent is clinically necessary during the randomization phase, this will be considered as a disease flare. The patient will be allowed to continue in their respective assigned group at the discretion of the treating physician and PI.

f. Medications and Therapies Prohibited for Concomitant Use:

a. Anti-B-cell therapy:

- i. Wash out of 5 therapeutic half-lives after prior B-cell therapy, or until pharmacodynamic effect would be minimal (e.g., 1 year following Rituximab)
 - IgG levels should be measured monthly in this situation
 - Benlysta should be discontinued in subjects with IgG levels <250 mg/dL associated with a severe or serious infection
- ii. If Rituximab use was medically indicated after the patient's enrolment to the clinical trial, the patient will no longer receive the investigational drug, but enhanced safety monitoring will be required.

b. Intravenous Cyclophosphamide

- i. 180 Days Prior to Belimumab
 - IgG levels should be measured monthly in this situation
 - Benlysta should be discontinued in subjects with IgG levels <250 mg/dL associated with a severe or serious infection

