2. Elevation of at least one muscle enzyme (creatinine kinase [CK]; myoglobin; alanine aminotransferase [ALT]; or aspartate aminotransferase [AST]) to a minimum level of 1.3 times the upper limit of normal.
3. Physician Global Assessment ≥ 2.0 cm using a visual analogue scale (VAS) 10.0 cm in length.
4. Patient Global Assessment ≥ 2.0 cm using a visual analogue scale (VAS) 10.0 cm in length.
5. Global extra muscular disease activity score ≥ 1.0 cm using a visual analogue scale (VAS) 10.0 cm in length. This score is based on the investigator's composite assessment of disease activity of the constitutional, cutaneous, skeletal, gastrointestinal, pulmonary and cardiac scales on the Myositis Disease Activity Assessment Tool (MDAAT).
6. HAQ disability index with a minimum value of 0.25.

The patient will be required to meet an MMT 8 score of $\leq 125/150$ as a major CSM criterion and at least 2 other CSM criteria to classify as an active disease.

In addition, for patients with ≥ 7 years of IIM, muscle biopsy or muscle MRI within 4 months prior to enrollment will be required to document active myositis to avoid enrolling patients with

significant index of damage/ muscle atrophy. This is not applicable to DM patients with a cutaneous VAS score of >3 cm on a 10 cm VAS scale (MDAAT).

Response rate: The response rate will be assessed by the percentage of patients meeting the definition of improvement (DOI). DOI is based on the definition of improvement developed by the International Myositis Assessment and Clinical Studies Group utilizing 6 core set measures.

DOI: DOI is defined as $\geq 20\%$ improvement in any 3 of the CSM, with no more than 2 CSM worsening by $\geq 25\%$ (excluding MMT)¹¹.

Definition of Worsening (DOW): Determination of worsening of the disease activity will be based on the definition of worsening (DOW) criteria developed by the International Myositis Assessment and Clinical Studies Group (IMACS) utilizing 6 core set measures¹¹:

1. worsening of Manual Muscle testing by $\geq 20\%$ and or Physician Global worsening of ≥ 2 cm on a 10 cm VAS or
2. Global extra muscular organ disease activity worsening by ≥ 2 cm on a 10 cm VAS on MDDAT, or
3. 3 of 6 CSM worse by $\geq 30\%$

Disease Flare: IIM Disease Flare is recorded when the patient:

1. reaches DOW;
2. new start or dose increase of corticosteroid or immunosuppressive agent for treatment of IIM after study week 8;

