3. an increased dose of corticosteroid before study week 8 and did not return to $<25\%$ above the baseline dose by week 12.

Endpoints:

1. **Primary Endpoint:**
 - a. Response rate at 40 weeks defined as percentage of patients meeting definition of improvement (DOI) in IIM patients treated with belimumab and standard therapy compared to the percentage of patients meeting DOI treated with placebo and standard therapy.
2. **Secondary Endpoints:**
 - a) Incidence of flares: flare rates during 40 weeks randomization period in patients with IIM treated with belimumab and patients treated with placebo and at week 64 in each group.
 - b) Time to achieve initial improvement defined as the time to reaching DOI.
 - c) Duration of improvement; quantified as the time from achieving improvement to the time of worsening or a disease flare. (Time from 1st DOI to 1st DOW or disease flare event). This will be based on the subset of subjects who achieve improvement.
 - d) Percent change in muscle enzyme levels (CPK and myoglobin) from baseline to week 40 and 64 in each respective group
 1. $<20\%$ reduction: no response
 2. 20-70% reduction: partial response
 3. $>70\%$ reduction: complete response
 - e) Percent change in manual muscle assessment (MMT-8) from baseline to week 40 and week 64 in each respective group.

- 1. <20% reduction: no response
- 2. 20-70% reduction: partial response
- 3. >70% reduction: complete response
- f) Percent change in prednisone dose from baseline to week 40 and week 64 in each respective group
- g) Proportion of subjects, among those on steroids at baseline, able to reduce the prednisone dose to ≤ 5 mg daily at week 40 and week 64 in each respective group.
- h) Flare rate in placebo group during the 40 week randomized treatment phase as compared to that group in the 20 week open label phase.
- i) Serious adverse event and adverse event rates
- j) Changes in B cell populations from baseline to week 40 and week 64
- k) Changes in autoantibody titers from baseline to week 40 and week 64
- l) Changes in immunoglobulin concentrations from baseline to week 40 and week 64

Inclusion Criteria:

Subjects enrolled in the study must meet the following inclusion criteria:

- 1) Adults ≥ 18 years of age
- 2) Have a diagnosis of:
 - a. definite or probable dermatomyositis (DM) by modified Bohan & Peter criteria or

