The Biostatistics Randomization Management System (BRMS) is a secure, HIPAA-compliant, web-based application that allows investigators to randomize subjects into randomized clinical trials (RCTs) using their personal computer. The BRMS allows for multi-center, stratified, and single/double blinded RCTs, using permuted blocks. Randomization notifications are automatically sent to the PI and other authorized personnel. Using BRMS is a good way to maintain compliance in RCTs.

Statistical Considerations

SPECIFIC STATISTICAL AIMS

The primary objective of the study is to compare subjects in the Belimumab group and subjects in the placebo group with respect to response (improvement) at week 40.

The specific aims of the study are to compare the two treatment arms (Belimumab vs. Placebo [P vs. B]), during the 40-week randomized phase of the study, with respect to the following:

1. Response at week 40.
2. Flare rates during the 40-week treatment period.
3. Time-to-achieve (initial) improvement during the 40-week randomized phase of the study
4. Duration of improvement during the 40-week randomized phase of the study, among those who achieved improvement (this is essentially a time-to-flare/relapse analysis from the time that you achieved improvement)
5. Change in muscle enzyme levels (CPK, myoglobin) from baseline to week 40
6. Change in MMT-8 from baseline to week 40
7. Change in prednisone dose from baseline to week 40

8. Proportion of subjects able to reduce prednisone dose to ≤ 5 mg at week 40
9. Change in B cell populations, immunoglobulin levels and BLys levels from baseline to week 40.
10. Change in autoantibody titers from baseline to week 40.
11. Rates of SAEs and AEs experienced

STATISTICAL METHODS

All subjects will be analyzed according to the intention-to-treat [ITT] principle. A subject will be considered evaluable and will be included in the intention-to-treat analysis if he/she received at least the first five of the planned infusions during the randomized phase of the study. Subjects who do not get the first five infusions will be considered ‘drop-outs’. It should be noted that the study protocol calls for patients remaining on their treatment assignment. However, adjustments in dosages of medications used in their ‘standard care’ are permitted during the first 8 weeks. Analyses that take into account the actual treatment received (e.g. accounting for compliance, etc.) will be carried out as a secondary analysis (per protocol [PP] analysis).

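### The flare rules behind secondary endpoints a, c and h conflict between sections, and endpoint h sets 40 weeks against a mislabelled 24-week phase with no stated method

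*Combined protocol and SAP*

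**What the plan says.** Flare enters secondary endpoints a (flare incidence), c (duration of improvement, ended by worsening or flare) and h (placebo-group flare rate, randomized versus open-label phase). The rules for it stand in several sections.

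- **Prednisone raised in weeks 0–8.** Study Design e, Concurrent Medications: "In this case, the dose of prednisone must be tapered (to less than or equal to 25% of the baseline dose) by week 12". It adds that "if the dose of prednisone cannot be tapered by week 12, the event will be considered as disease flare at that time". The same section also says: "The prednisone dose will remain stable until week 24 of the study, at which time a taper will be allowed". Definitions, Disease Flare, item 3 instead counts a flare when the dose did not come back to below 25% "above the baseline dose by week 12".
- **Immunosuppressive (IS) agents.** Concurrent Medications says of an IS increase or a new agent that if it "is clinically necessary during the randomization phase, this will be considered as a disease flare". Disease Flare item 2 counts a "new start or dose increase of corticosteroid or immunosuppressive agent for treatment of IIM after study week 8". Statistical Methods says that standard-care dose adjustments "are permitted during the first 8 weeks", without saying whether they count as flares.
- **Pulse steroids.** Concurrent Medications: "the use of pulse steroids at any time during the study will be considered a disease flare". The Disease Flare definition does not name pulses.
- **Open-label phase.** Study Design d (Blinding) and endpoint h call it 20 weeks. Study Design a runs it from week 40 to week 64.
- **Analysis.** The specific aims cover only belimumab versus placebo in the 40-week phase. Statistical Methods item 2 compares the proportion with any flare and adds an optional incidence density ratio. Both are between arms, over 40 weeks.

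**The concern.** The same patient can be a flare or not depending on which section a site or analyst follows. With 15 patients per arm, a few such cases can move a flare proportion visibly, and choosing the rule after unblinding would leave an avoidable analyst decision. Endpoint h has a further problem. It compares two windows of different length, one of them misstated, and no denominator or method is given. A patient watched for 24 weeks has less opportunity to flare than one watched for 40.

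**Working it through.** **Plan's own figures.** The plan gives no flare rate and no power for flare, so there is nothing to reproduce on this endpoint. Its only sizing figure, 15 per group for 5% versus 50% response, reproduces with the pooled-variance two-proportion formula without continuity correction. It does not use flare.

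**Step 1: the week-12 prednisone rule.** Let B be the baseline dose (at most 15 mg in Concurrent Medications and inclusion criterion 8) and D the dose at week 12. Concurrent Medications: flare if D > 0.25 × B. Disease Flare item 3: flare if D ≥ 1.25 × B.

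| B | 0.25 × B | 1.25 × B |
|---|---|---|
| 5 mg | 1.25 mg | 6.25 mg |
| 10 mg | 2.5 mg | 12.5 mg |
| 15 mg | 3.75 mg | 18.75 mg |

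The cut-offs differ five-fold (1.25/0.25). Any dose between them gets opposite labels, including D = B, a patient exactly back at baseline. The 25%-of-baseline reading would also require a deep cut by week 12 in a section that holds prednisone stable to week 24, so it is almost certainly a slip.

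**Step 2: the other triggers side by side.** Assume the patient does not also meet the definition of worsening (DOW), which is a flare in any case.

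| Event | Concurrent Medications | Disease Flare definition |
|---|---|---|
| IS start or increase for myositis, weeks 0–8 | flare | not a flare |
| Same, after week 8, randomized phase | flare | flare (item 2) |
| Same, open label | silent | flare (item 2) |
| Pulse for myositis after week 8 | flare | flare (item 2) |
| Pulse in weeks 0–8, not resolved by week 12 | flare | flare (item 3) |
| Pulse in weeks 0–8, resolved by week 12 | flare | not a flare |
| Pulse after week 8 for another reason | flare as written | not a flare |

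The conflicts are therefore the first row and the last two. On the last row, Concurrent Medications also excuses prednisone increases for other events if the baseline dose is restored within 10 days, but its pulse rule carries no such exception. One reclassified patient is 1/15 = 6.7 percentage points of an arm.

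**Step 3: phase length and ascertainment.** 64 − 40 = 24 weeks, not 20. Core-set visits, which detect DOW, fall at weeks 8, 16, 24, 32 and 40 (5/40 = 0.125 per week) and then at weeks 52 and 64 (2/24 = 0.083 per week).

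**Step 4: what window length alone would do to h.** Assume that h is analysed as the proportion with any flare, that the hazard is constant and that the drug has no effect. With proportion p flaring in 40 weeks, the open-label proportion is 1 − (1 − p)^(24/40). The values of p are assumptions.

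| p over 40 weeks | over 24 weeks | relative fall |
|---|---|---|
| 20% | 12.5% | 37% |
| 40% | 26.4% | 34% |
| 60% | 42.3% | 30% |

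For prednisone increases excused in weeks 0–8, the countable randomized time is nearer 32 weeks: 1 − 0.60^(24/32) = 31.8%, a fall of 20% from 40%.

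**Step 5: the same data per person-time.** For p = 40% the weekly hazard is −ln(0.60)/40 = 0.0128 in both phases, so the rate ratio is 1.0. The apparent fall disappears.

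**The case against.** The best defence has three parts. First, the 25%-of-baseline wording is an obvious drafting error, and the formal Disease Flare definition gives the workable rule. That stands, but the faulty text is the medication instruction that sites follow, so it needs correcting. Second, Statistical Methods item 2 already offers an incidence density ratio, and endpoint h is called a rate with both phase lengths on its face. That partly stands: the method could be extended to h, but it is stated only between arms over 40 weeks and is described in days of flare. Third, h is an uncontrolled comparison in about 15 patients, so elaborate trigger-by-trigger accounting is not warranted. That stands too.

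Three stronger readings are tempting and unsupported:

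- That IS changes in the open-label phase are in dispute. Disease Flare item 2 covers everything after week 8, and no section contradicts it there.
- That the flare definition misses pulse steroids altogether. It misses only the name; most pulses are caught by items 2 and 3.
- That h is biased downward by a known amount. The plan does not say h is a proportion and gives no flare rates. Prednisone taper is allowed from week 24, so all of open label lies in the taper period and the net direction is uncertain. The 20-week figure may also describe the span from the first to the sixth monthly infusion (weeks 40 to 60), although observation still runs to week 64.

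**Conclusion.** The concern holds in limited form and should be fixed. One stated rule (25% of baseline) and one stated duration (20 weeks) are wrong as written. Two narrow classes of event, IS changes in weeks 0–8 and pulses that are early and resolved or not for myositis, have contradictory flare status. Endpoint h has no stated analysis. How many patients are affected cannot be known from the documents. The 40%-to-26% illustration rests on an any-flare proportion, a constant hazard and no drug effect, none of which the plan states.

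A reader might infer that the trial's main result is compromised. It is not: the primary endpoint is the definition of improvement at week 40 and does not use flare, and the sample size is unaffected. In the blinded between-arm flare comparison, inconsistent classification is mainly noise, because sites apply whichever rule they follow without knowing the arm.

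**What to change.** Before unblinding:

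1. Correct Concurrent Medications so that an early prednisone increase must return to less than 25% above the baseline dose by week 12.
2. Make the Disease Flare definition the single source. Choose one IS rule for weeks 0–8 (excused or counted), add pulse steroids explicitly and say whether use for other conditions counts. Align Concurrent Medications and Statistical Methods to it.
3. State the open-label observation window as 24 weeks (weeks 40–64).
4. Analyse h as flares per person-time at risk, extending the incidence density approach of Statistical Methods item 2 to the two phases of the placebo group. Label it an uncontrolled before-after comparison, with core-set visits every 12 rather than every 8 weeks and open label lying wholly in the taper period.

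The cost is protocol and SAP wording plus two sponsor decisions (IS rule, pulse rule). Endpoint c already needs flare dates, so no new data collection is expected; the sponsor should check that the trigger for each flare is recorded as well. The sparser visits and the taper remain as stated limitations of h.

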The Biostatistics Unit at the Feinstein Institute for Medical Research [BU-FIMR] will develop a web based randomization plan for the study. A randomization schema will be generated by the BU-FIMR for each participating site using the method of permuted blocks. Subjects will be randomly assigned in a 1:1 ratio to either Belimumab or Placebo, according to two stratification variables, namely, disease type (Polymyositis or Dermatomyositis) and disease severity (severe or less severe). The Biostatistics Randomization Management System (BRMS) is a secure, HIPAA-compliant, web-based application that allows investigators to randomize subjects into randomized clinical trials (RCTs) using their personal computer. The BRMS allows for multi-center, stratified, and single/double blinded RCTs, using permuted blocks. Randomization notifications are automatically sent to the PI and other authorized personnel. Using BRMS is a good way to maintain compliance in RCTs.

c. Stratification:

Randomization will be according to the two important stratification variables: disease type (Polymyositis vs. Dermatomyositis) and disease severity (severe vs less severe) and will occur at week 0 (first infusion). The number of immunosuppressive agents used by the patient over the last year (corticosteroids are not included) will be used as a surrogate of disease activity: one or less IS agent over last year versus more than 1 IS agent over last year.

d. Blinding:

This is a double-blind study; both the investigator and the patient will be blinded to the treatment assignment in the randomized phase of the trial. At the end of the 40 week randomized treatment phase all subjects will start the 20 week open label phase and therefore the drug will be dispensed in the unblinded fashion.

For each study site, there will be a designated unblinded research coordinator (URC) and a blinded research coordinator (BRC). The URC will be responsible for obtaining randomization assignments from the BU-FIMR and will oversee the preparation of infusions prior to drug administration. The BRC will be responsible for coordinating patient visits and administration or the infusion (infusion will be masked and not identifiable through any physical characteristics such as color or consistency, as the drug is of a powder form mixed in saline solution).

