
1. For specific aim 1, the two treatment arms [B vs. P] will be compared with respect to the proportion of subjects who respond to treatment at 40 weeks (improvement according to definition), using either a chi-square test or Fisher’s exact test, as appropriate.
2. For specific aim 2, either a chi-square test or Fisher’s exact test, as appropriate, will be conducted to compare the proportion of subjects who had any flares during the 40-week randomized phase. For this analysis, each subject will be categorized at the end of 40 weeks as having had one or more flares or not having had any flares. In addition, we can also examine the total number of days that a subject had a specific flare during the course of the 40-week treatment, and compare the two treatment arms using the ‘Incidence density ratio’ method.
3. For specific aim 3, standard methods for survival analysis will be carried out. The Kaplan-Meier (KM) product limit method will be used to estimate overall “time-to-achieve (initial) response/improvement”. Ninety-five percent confidence intervals will be calculated using Greenwood’s formula for computing the standard error. Subjects who have not achieved improvement as of week 40 will be considered ‘censored’ for the event (event=improvement/response).
4. For specific aim 4, similar methods as indicated for specific aim 3 will be conducted. The analysis for this aim will be limited to the subset of subjects in each treatment arm who show improvement at anytime during the randomized phase of the trial. A subject who has not flared/worsened/relapsed as of week 40 will be considered ‘censored’ for the event (event=flare/relapse).
5. For specific aims 5, 6, 7, 9 and 10, each of the outcome variables of interest (uncensored continuous or categorical) will be analyzed separately, using a mixed model approach to repeated measures analysis of variance (MMRMANOVA) with the main effects of treatment arm (B vs. P), Disease type (PM vs DM), Disease Severity (Severe vs. Less Severe) and time (baseline vs. 40 weeks). If feasible, statistical interactions between

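### After a prednisone increase unrelated to myositis, the protocol names the baseline dose as the 10-day target even for patients already tapered below it, which can erase a recorded steroid reduction at week 40

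*Combined protocol and SAP*

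**What the plan says.** Three parts of the combined protocol and SAP bear on this point.

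- **Taper.** Study Design, e. Concurrent Medications, Corticosteroids: "The prednisone dose will remain stable until week 24 of the study, at which time a taper will be allowed". The decision is left to the site investigator and the principal investigator, and no schedule is given.
- **Increase for another reason.** In the same section, the scope of the rule is "An increase of the prednisone dose at any time during the study for an event other than worsening of IIM disease activity", so it also covers the weeks after tapering may begin. What follows from such an event is that it "will require the patient to return to the baseline dose of prednisone within 10 days, without accounting the event as a disease flare". There is no exception for patients below baseline and no mention of the pre-event dose.
- **What is measured.** Steroid sparing is study objective c. Secondary endpoint f is "Percent change in prednisone dose from baseline to week 40 and week 64 in each respective group". Secondary endpoint g is the share of baseline steroid users who get to 5 mg daily or less at the same two visits. The randomized comparisons, both at week 40, are aim 7 ("Change in prednisone dose from baseline to week 40") and aim 8 ("Proportion of subjects able to reduce prednisone dose to" 5 mg or less). Statistical Methods item 5 analyses aim 7 "using a mixed model approach to repeated measures analysis of variance". Item 6 compares the aim 8 proportions with a chi-square or Fisher's exact test.

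**The concern.** Up to week 24 the dose is held stable, so baseline is normally also the pre-event dose and the rule works. Once a taper has begun, the two doses differ and the rule names the higher one. The sentence therefore sets the quantity that endpoints f and g record. A patient who had achieved a reduction, then needed a short steroid course for some other illness, could be at the full baseline dose at week 40 and be fully compliant.

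The Statistical Methods section has no rule for prednisone doses altered by a non-IIM event, so the analysis does not correct for this. Sites may also differ: one may restore the tapered dose and another the baseline dose, both within protocol. At stake is the accuracy of the steroid-sparing results, not the primary comparison.

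**Working it through.** The plan gives no figure for this rule, so there is none to reproduce. The check is what f and g record under each return dose.

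**Inputs.** Baseline prednisone up to 15 mg daily (Corticosteroids; inclusion criterion 8). Taper from week 24 and 10 days to return (Corticosteroids). Threshold of 5 mg for g (Endpoints). The dose pairs below are assumed examples within the 15 mg limit.

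**Formulas.** With baseline B and dose D at the visit, f = (D - B)/B, and g is met if D is 5 mg or less. For a patient tapered to T before the event, compare D = T with D = B. At D = B, f is always (B - B)/B = 0%.

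| B (mg) | T (mg) | f at T | f at B | g at T | g at B |
|---|---|---|---|---|---|
| 15 | 10 | (10-15)/15 = -33.3% | 0% | not met | not met |
| 15 | 5 | (5-15)/15 = -66.7% | 0% | met | not met |
| 10 | 5 | (5-10)/10 = -50% | 0% | met | not met |
| 5 | 2.5 | (2.5-5)/5 = -50% | 0% | met | met |
| 15 | 0 | (0-15)/15 = -100% | 0% | met | not met |

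The last row is the extreme: 15 mg daily above the pre-event dose. Endpoint f changes in every row. Endpoint g changes only where B is above 5 mg and T is 5 mg or less.

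**Scale for g.** If all 15 planned patients in an arm were on steroids at baseline, one change in g would move that arm's proportion by 1/15 = 6.7 percentage points; with fewer steroid users in the denominator it would move more. This gives the weight of one patient and is not a forecast. No equivalent is given for aim 7, because that comparison rests on a mixed model and the number of events is unknown.

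**Window before week 40.** Week 24 is day 24 x 7 = 168 and week 40 is day 40 x 7 = 280, so 280 - 168 = 112 days. An event starting after day 280 - 10 = 270 can leave the dose raised at week 40 even under better wording, because 10 days are allowed. Better wording can therefore help for events starting within at most 270 - 168 = 102 of the 112 days. This is an upper bound, since no taper need have begun by day 168.

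**Week 64.** The per-patient arithmetic is the same, but "At the end of the 40 week randomized treatment phase all subjects will start the 20 week open label phase", so every patient is by then on open-label belimumab and the week 64 result is descriptive.

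**The case against.** The strongest reply is that baseline is meant as a ceiling. The sentence sits among rules on which increases count as a flare, and the flare definition also uses baseline as a reference for an upper limit. As a target it gives odd results: a patient tapered from 15 to 5 mg and raised to 10 mg for another illness would have to go up to 15 mg. The ceiling reading is reasonable, and under it the protocol does not require a dose above the pre-event dose. It still permits one, so a patient left at baseline complies.

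Second, nothing stops the investigators from tapering again. Infusions fall at weeks 24, 28, 32 and 36, which leaves several visits after an early event. This stands, and it is why the effect is conditional. But re-tapering is discretionary and unscheduled, and a late event leaves little time.

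Third, if the patient takes the baseline dose at week 40, 0% is the correct value of endpoint f as defined. That also stands: the recorded number is not wrong. The difficulty is that a protocol sentence, and not the course of IIM, may have set the dose, which weakens the endpoint as a measure of steroid sparing.

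Fourth, harm needs a chain: steroids at baseline, a taper, a later non-IIM increase, a return to baseline and no re-taper by the visit. The documents give no frequency for the steps after baseline.

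A reader might infer that the steroid-sparing comparison is biased against belimumab. The documents do not support that. The rule applies to both blinded arms, and a smaller difference would follow only if belimumab patients tapered more, which is an assumption. Nor does the text support the view that every tapered patient with such an event fails endpoint g, or that the primary endpoint is touched.

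**Conclusion.** The point holds in a limited form. The rule names a dose that is too high for a patient who has tapered, or at least allows that dose, and so works against objective c. For an affected patient still at baseline at week 40, f reads 0% whatever reduction had been reached, and g is lost only when the taper had crossed from above 5 mg to 5 mg or less.

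This rests on reading baseline as study baseline, which is how endpoint f and the flare definition use it and which no section redefines, and on no re-taper by the visit. The number of events may be small or zero, and no arm-level shift or direction of bias is claimed. The primary endpoint, the flare definition and the sample size of 15 per arm are unaffected. It is a cheap improvement, not a threat to the trial's main conclusion.

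**What to change.** Replace the end of the sentence with wording such as:

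> *...the patient must be back at no more than the baseline dose by day 10, in which case the event is not counted as a disease flare. A patient who had tapered below baseline returns to the dose taken immediately before the event within the same 10 days, unless the investigator documents a clinical reason for a slower return.*

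The no-flare condition stays tied to baseline, so the allowance is not narrowed and a slower return in a tapered patient does not become a flare. Nothing changes for patients who have not tapered.

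The cost is one protocol sentence, with no new visit or analysis; the only added record is the investigator's reason when the return is slower. The small downside is somewhat tighter steroid management in tapered patients who have just needed extra prednisone, which the documented-reason clause limits. Events in the last 10 days before week 40, and documented slower returns, can still leave the dose raised at that visit.
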